### Study Specific Definitions

#### ACT

Active clotting time

#### Blanking Period

The blanking period is the 90 days immediately following the index ablation procedure. During this time, recurrences of arrhythmias are not counted towards the trial effectiveness end point.

#### Device-Related

Exposure to the TactiCath SE device has occurred and the device is more likely than other alternative causes to be responsible for the adverse event or it cannot be ruled out that the device is not responsible for the adverse event.

*Documentation of AF-related Symptoms*

Documentation by a physician evaluating the patient that the patient experiences symptoms that could be attributable to AF. This does not require a time-stamped ECG, Holter, or event monitor at the precise time of symptoms.

*Index Ablation Procedure*

This refers to the initial procedure where ablations were performed to treat atrial fibrillation within this trial.

*Long-standing Persistent Atrial Fibrillation*

Long-standing persistent AF is defined as continuous AF of greater than 12 months duration.

*NIHSS*

This is the National Institutes of Health Stroke Scale. It is a standard assessment for stroke which can be accessed at the following website: [https://www.ninds.nih.gov/sites/default/files/NIH\\_Stroke\\_Scale.pdf](https://www.ninds.nih.gov/sites/default/files/NIH_Stroke_Scale.pdf)

*Paroxysmal Atrial Fibrillation*

Paroxysmal AF is defined as AF that terminates spontaneously or with intervention within 7 days of onset.

*Persistent Atrial Fibrillation*

Persistent AF is defined as continuous AF that is sustained beyond 7 days.

*Physical Exam*

This is a standard of care physical exam, conducted by an investigator that includes a neurological assessment.

*Procedure-Related*

Determination of TactiCath SE procedure relationship includes assessment of AEs for relationship to any of the following: discontinuation of anticoagulation medication for the TactiCath SE procedure, administration of local or general anesthesia, or the TactiCath SE procedure. Relationship of TactiCath SE procedure will be assessed regardless of the temporal relationship to the TactiCath SE procedure.

*Symptomatic AF/AFL/AT*

AF/AFL/AT that results in symptoms that are experienced by the patient. These symptoms can include but are not limited to palpitations, presyncope, syncope, fatigue, and shortness of breath.

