#### 4.3.1 Primary Safety Endpoint

The primary safety endpoint is the rate of device or procedure-related serious adverse events occurring within 7 days of the index procedure. SAEs related solely to arrhythmia recurrence (without coexisting conditions such as thromboembolism, worsening heart failure, etc.) will not be considered primary safety endpoint events. The SAEs that will be included in this endpoint are:

- Atrial-esophageal fistula
- AV block
- Cardiac perforation/ Tamponade
- Death
- Diaphragmatic paralysis
- Gastroparesis
- Hospitalization
- Myocardial Infarction
- Pericarditis
- Pneumothorax
- Pulmonary edema
- Pulmonary vein stenosis
- Stroke
- Thromboembolism
- Transient ischemic attack
- Vascular access complication

These events must meet the criteria listed in Appendix C to be included in the primary endpoint as adjudicated by the clinical events committee (CEC). Atrial-esophageal fistula, cardiac perforation/tamponade, and pulmonary vein stenosis that occur >7 days post procedure through 30 days will also contribute to the primary endpoint.

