### 6.1.1 Primary Safety Endpoint Hypothesis

The performance goal is set at 16.2% based on experience with the TactiCath ablation catheter (a prior generation of the TactiCath SE catheter, see below for further detail). The hypothesis is formally expressed as:

$$H_0: P \geq 16.2\%$$

$$H_a: P < 16.2\%$$

where P is the percentage of subjects with a primary safety endpoint event. The hypothesis will be tested based on a one-sided exact test of binomial proportions at the one-sided 0.05 alpha level. Rejection of the null hypothesis will indicate study success. The performance goal of 16.2% is set to be equal to that for previous generations of the TactiCath catheter.

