#### 6.1.1.1 Analysis Methodology

The primary safety endpoint event rate will be calculated based on the number of subjects experiencing a primary safety endpoint divided by the total number of subjects in the analysis population. Relatedness of the event to the catheter and to the procedure will be determined by the CEC. The null hypothesis will be rejected if the upper bound of the one-sided 95% confidence interval for the proportion of subjects with a primary safety endpoint is less than 16.2%. Subjects without an event that are lost to follow up without a visit at or beyond their 30-day follow up visit window will be excluded from this analysis.

[REDACTED]

[REDACTED]

[REDACTED]

[REDACTED]

[REDACTED]

[REDACTED]

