### 8.2 Safety Reporting

Safety surveillance within this study and safety reporting performed both by the investigator and Sponsor starts as soon as the subject is enrolled. Safety surveillance and reporting will continue until the last investigational visit has been performed, the subject is deceased, the subject concludes their participation in the clinical investigation or the subject withdraws from the clinical investigation. All adverse event data including deaths will be collected throughout the time period defined above and will be reported to the Sponsor on an eCRF. Additional information on an adverse event should be updated within the appropriate case report form. Unchanged, chronic, non-worsening or pre-existing conditions are not AEs and should not be reported.

For the purposes of this clinical investigation, the following events will be reported (see Appendix B for definitions):

- Serious adverse events
- Adverse events that are considered related to either the ablation catheter or the ablation procedure by the investigator

Recurrence of AF, AFL, or AT are not considered reportable adverse events unless they occur in a severity, frequency, or other manner that is significantly worse than the subject's baseline condition. These are considered lack of effectiveness and will be reported as a recurrence on the appropriate case report form.

Non-cardiac related abnormal laboratory values will not be considered AEs unless:

- The investigator determined that the value is clinically significant,
- The abnormal lab value required intervention, or
- The abnormal lab value required subject termination from the study.

The investigator should report all SAEs to the Sponsor as soon as possible but no later than outlined below.

Clinical Site	Reporting timelines
All Sites	SAEs must be reported to the Sponsor no later than 3 calendar days from the day the site personnel became aware of the event or as per the investigative site's local requirements, if the requirement is more stringent.

The date the site staff became aware the event met the criteria of an SAE must be recorded in the source document. The Investigator will further report the SAE to the local IRB/EC according to the institution's IRB/EC reporting requirements.

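### A stray negative in the Device-Related definition means that, as written, it excludes no adverse event after exposure

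*Protocol*

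**What the plan says.** Protocol Appendix B, under Device-Related, requires exposure to the TactiCath SE and then gives two alternatives joined by *or*. The first is that "the device is more likely than other alternative causes to be responsible for the adverse event". The second is that "it cannot be ruled out that the device is not responsible for the adverse event". Neither the protocol nor the SAP defines the term anywhere else.

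The term is used in three places:

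- **Primary safety endpoint.** Protocol 4.3.1 defines it as the "rate of device or procedure-related serious adverse events occurring within 7 days of the index procedure", and SAP 4.1 and 5.1 follow. Protocol 6.1.1.1 adds: "Relatedness of the event to the catheter and to the procedure will be determined by the CEC". There is also a filter by event type: "These events must meet the criteria listed in Appendix C to be included in the primary endpoint".
- **Descriptive endpoints 3 and 4.** Protocol 6.1.5.1 and 6.1.6.1, with SAP 6.3.1 and 6.4.1, tabulate adverse events by seriousness and relatedness.
- **Site reporting.** Protocol 8.2 points to Appendix B for definitions. Apart from SAEs, it asks sites to report only "Adverse events that are considered related to either the ablation catheter or the ablation procedure by the investigator".

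Appendix B defines Procedure-Related separately. That entry covers interruption of anticoagulation for the procedure, anesthesia, and the procedure itself, whatever the timing. It lists what to assess but sets no threshold for causality.

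**The concern.** A relatedness definition has to separate events that count from events that do not. The second limb tests whether the device might be innocent, when its evident purpose is to test whether the device might be responsible. An assessor who applied the text as printed would have to call a clearly unrelated event device-related.

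For the primary safety endpoint, device-relatedness alone is enough to satisfy the causal condition, so a listed event with no link to catheter or procedure could be counted. For descriptive endpoints 3 and 4, a device split that puts every event after exposure on one side carries no information. For site reporting, the investigator's judgment decides which non-serious events are reported at all. A site that applies the text literally and one that corrects it in its head would therefore send in different sets of events.

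**Working it through.** The point is about wording, so the plan has no figure to reproduce. The check has two parts.

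**1. What the definition admits.** Take an event after exposure, with exposure governing both limbs. Let p be the assessor's probability that the device is responsible.

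- First limb (device likelier than the alternatives): p > 0.5.
- Second limb as printed (innocence of the device not ruled out): p < 1.
- Second limb without the *not* before *responsible* (responsibility not ruled out): p > 0.

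| p | As printed: p > 0.5 or p < 1 | Without the *not*: p > 0.5 or p > 0 |
|---|---|---|
| 0 | related | **not related** |
| 0.1 | related | related |
| 0.5 | related | related |
| 0.9 | related | related |
| 1 | related (first limb only) | related |

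As printed, the second limb fails only at p = 1, and the first limb covers that case. Together they cover the whole range from 0 to 1. The printed and amended definitions differ only at p = 0, where device causation has been ruled out.

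**2. Which of those events reach the primary endpoint.** For the printed wording to change the count, one event has to meet all of these conditions:

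1. It is an SAE of a type listed in protocol 4.3.1.
2. It meets its row in Appendix C.
3. It falls within 7 days. Atrial-esophageal fistula, perforation/tamponade and pulmonary vein stenosis count through 30 days.
4. Device causation has been excluded (p = 0).
5. Procedure causation has also been excluded. The endpoint takes device- *or* procedure-related events, so an event related to the procedure counts under either wording.

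The Appendix C rows differ in how far they protect against an unrelated event:

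| Appendix C row | Causal wording in the row |
|---|---|
| Hospitalization | Requires a cause related to the ablation procedure |
| AV block | Excludes vasovagal and medication causes |
| Vascular access complications | Tied to vascular access |
| Death | None |
| Myocardial infarction | None as to device or procedure |
| Thromboembolism | None as to device or procedure |

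For the last three, the relatedness determination is the main gate. An unrelated death, infarction or thromboembolism in the first week is the kind of event the printed definition would add.

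**The case against.** The strongest reply is that this is an obvious slip. The first limb is an ordinary causality test, the intended meaning of the second is plain, and the CEC makes the final call under a charter that may carry a sound definition. The two wordings differ only on events where the device has been ruled out, and many listed events would enter as procedure-related in any case. Applied literally, the error makes the 16.2% goal harder to meet. It cannot hide harm or create a false success. Descriptive endpoints 3 and 4 carry no hypothesis test.

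Most of this stands and sets the severity. It does not remove the defect: the only definition in either document states a rule that cannot be applied as written.

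A reader might draw three stronger conclusions that the documents do not support:

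- **That every unrelated listed SAE within 7 days would be added.** This ignores the Appendix C criteria, the causal wording in the Hospitalization row and the separate procedure-related route.
- **That one misclassified event measures the damage.** With 140 subjects (protocol 6.5), the exact one-sided 95% upper bound is the 0.95 quantile of Beta(x + 1, 140 − x). For x = 15 (15/140 = 10.7%) it is 16.02%, which passes; for x = 16 it is 16.84%, which fails. That is how any exact test behaves at its boundary. It says nothing about how many events this wording would add.
- **That adjudication rests on an unwritten rule.** The CEC charter is not among the documents, so this is unknown.

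**Conclusion.** The definition is wrong as written: a drafting error in an operative definition, of low severity. Only the second limb is reversed, but the *or* lets it absorb the whole definition, so every adverse event after exposure is device-related on a literal reading.

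For the primary safety endpoint, the exposure is confined to listed SAEs that meet Appendix C in the window and have had both device and procedure causation excluded. Literal use could only raise the event count. Its size cannot be stated, because neither document gives an expected number of such events. The device split in descriptive endpoints 3 and 4 would be uninformative, and reporting of non-serious events would depend on how each site reads the clause.

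This assumes that exposure governs both limbs and that sites and the CEC work from Appendix B. If the charter has its own correct definition, the adjudicated primary endpoint is protected, but the investigators' reporting decisions still rest on Appendix B.

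**What to change.** In the second limb of Device-Related, delete the *not* that stands before *responsible*, so that an event counts when the device's responsibility cannot be excluded. Confirm that the CEC charter and the eCRF guidance use the same text.

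The amended definition remains broad, since any event with a residual possibility of device causation still counts. It also makes the first limb redundant, because p > 0.5 implies p > 0; that is harmless. The cost is one deleted word and a check of two supporting documents. No endpoint, sample size, analysis or procedure changes.

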## Appendix C Primary Safety Endpoint Criteria

The following criteria will be used by the CEC to determine whether or not the events listed below constitute a device or procedure related serious adverse event included in the primary endpoint.

**Table 4: Primary Safety Endpoint Criteria**

Primary Serious Adverse Event	Criteria
Atrial esophageal fistula	Development of a connection between the atrium and the lumen of the esophagus
AV block	New, persistent 2 nd or 3 rd degree AV block not attributable to a vasovagal reaction or medication effect and requiring permanent pacing
Cardiac Perforation / Tamponade	Pericardial effusion that results in hemodynamic compromise, requires elective or urgent pericardiocentesis, or results in a 1-cm or more pericardial effusion as documented by echocardiography.
Death	Adverse event resulting in subject death
Diaphragmatic paralysis	Change in baseline diaphragmatic function as evidenced by elevation of a hemi-diaphragm above its normal position or loss of normal respiratory excursion but not due to a pulmonary process such as atelectasis and persisting longer than the end of the procedure
Gastroparesis	Vagal nerve injury that results in gastric dysmotility requiring intervention or hospitalization
Hospitalization (initial or prolonged)	Adverse event leading to new hospital admission or prolongation of initial hospital stay beyond expected timeframe due to ablation procedure-related cause. Excludes hospitalization solely for arrhythmia recurrence.
Myocardial Infarction	Irreversible necrosis of heart muscle secondary to prolonged ischemia with at least one of the following three criteria: 
 
• Detection of ECG changes indicative of new detection of ECG changes indicative of new ischemia (new ST-T wave changes or new LBBB) that persist for more than 1 hour
 
• Development of new pathological Q waves on an ECG
 
• Imaging evidence of new loss of viable myocardium or new regional wall motion abnormality
 

Pericarditis	Inflammation of the pericardium resulting in chest discomfort/pain associated with either pericardial rub and/or ECG changes that requires or prolongs hospitalization
Pneumothorax	Abnormal collection of air in the pleural space between the lung and the chest wall that prolongs hospital stay (for observation) or requires surgical intervention or chest tube placement
Pulmonary edema	Excess fluid in the lungs that includes all of the following: 
 
• Symptoms (e.g. dyspnea)
 
• Physical findings (e.g. rales, hypoxemia)
 
• Radiologic findings
 
• Respond to diuretic therapy
 
• Require hospitalization
 

Pulmonary Vein stenosis	Reduction in the diameter of a pulmonary vein (PV) or PV branch >70% confirmed via imaging (CT or MRI)
Stroke	Brain disorder involving loss of brain functions (that persists for > 24 hours) that occur when the blood supply to any part of the brain is interrupted as determined by the consulting neurologist
Thromboembolism	An arterial or venous thrombus that results in deep vein thrombosis, pulmonary embolism, or peripheral arterial embolism
Transient ischemic attack	Acute episode of temporary (< 24 hrs.) and focal loss of cerebral function of vascular (occlusive) origin as determined by the consulting neurologist
Vascular access complications	Adverse event related to vascular access requiring surgical repair, blood transfusion (e.g., groin hematoma, AV fistula) or significant intervention such as thrombin injection (e.g., pseudoaneurysm)

**Appendix D Labels**

Sample Instructions for Use available upon request under separate cover.

**Appendix E Sample Informed Consent Form**

Provided upon request under separate cover.

## 1 INTRODUCTION

This document is a statistical analysis plan for the TactiSense IDE trial (SJM-CIP-10216 Ver E).

## 2 TRIAL OBJECTIVES

The objective of this clinical trial is to demonstrate the acute safety and effectiveness of ablation with the TactiCath™ Contact Force Ablation Catheter, Sensor Enabled™ (TactiCath SE) for the treatment of drug refractory recurrent symptomatic PAF and is intended to support market approval of the TactiCath SE ablation catheter in the United States.

## 3 TRIAL DESIGN

This is a prospective, multi-center, single-arm clinical trial to evaluate the acute safety of the TactiCath SE catheter for the treatment of paroxysmal atrial fibrillation (PAF) against a performance goal. One hundred fifty six-(156) subjects will be enrolled at up to 35 investigational sites in the US, Europe, and Australia. Only sites that enroll at least one subject will be part of the analysis population. No center may contribute more than 20% of the total number of enrollments without sponsor pre-approval to exceed this proportion and at least 50% of subjects must be from the United States.

In addition to PVI, subjects with documented atrial flutter, AT or other SVT (spontaneous or induced) may undergo additional targeted ablation as clinically indicated.

**[REDACTED]** Subjects will be followed for 12 months after the index ablation procedure and then exit the clinical trial. **[REDACTED]** The pre-market approval (PMA) clinical report will be submitted when at least 140 subjects have been enrolled, had the investigational catheter inserted into their vasculature and either experienced an event as defined in CIP section 4.3.1, completed their 30 day follow up visit, or have been lost to follow up per CIP section 5.7.

A CEC will be responsible for providing an independent review and adjudication of adverse events. The primary function, responsibilities and membership of the CEC will be described in detail in a CEC charter.

## 4 TRIAL ENDPOINTS

There are two primary endpoints and ten descriptive endpoints for this trial. Since both primary endpoints must be met to declare a successful trial, no adjustments for multiplicity are required.

### 4.1 Primary Safety Endpoint

The primary safety endpoint is the rate of device- or procedure-related serious adverse events occurring within 7 days of the index procedure. SAEs related solely to arrhythmia recurrence (without coexisting conditions such as thromboembolism, worsening heart failure, etc.) will not be considered primary safety endpoint events. The SAEs that will be included in this endpoint are:

- Atrial esophageal fistula

## Statistical Analysis Plan

- AV block
- Cardiac Perforation/Tamponade
- Death
- Diaphragmatic paralysis
- Gastroparesis
- Hospitalization
- Myocardial Infarction
- Pericarditis
- Pneumothorax
- Pulmonary edema
- Pulmonary vein stenosis
- Stroke
- Thromboembolism
- Transient ischemic attack
- Vascular access complication

These events must meet the criteria listed in Appendix C of the CIP to be included in the primary endpoint and will be adjudicated by an independent clinical events committee (CEC). Atrial-esophageal fistula, cardiac perforation/tamponade, and pulmonary vein stenosis that occur >7 days post procedure through 30 days will also contribute to the primary endpoint.

#### 4.2 Primary Effectiveness Endpoint

The primary effectiveness endpoint is Acute Procedural Success, where acute procedural success is defined as confirmation of entrance block in all pulmonary veins.

#### 4.3 Descriptive Endpoints

There are ten types of descriptive endpoints. Descriptive endpoints are reported using summary statistics and no hypothesis testing will be performed.

1. Ablation data collected during the procedure, including:
  - Power
  - Temperature
  - Irrigation flow rate
  - Contact force
  - Procedure time
  - Total ablation time
  - Total fluoroscopy time

## Statistical Analysis Plan

- Total RF application time
  - Usage of Automark
2. Proportion of index cases achieving achieving  $\geq 90\%$  lesions with  $\geq 10\text{g}$  contact force
  3. Serious adverse events and adverse events related to the procedure and/or ablation catheter through 30 days post index ablation
  4. Serious adverse events and adverse events related to the procedure and/or ablation catheter through 1 year post index ablation
  5. One-year success defined as freedom from symptomatic AF/AFL/AT lasting at least 30 seconds without a new Class I or III AAD or a higher dosage of pre-existing AAD as assessed from the end of the 3-month blanking period to 12 months following the ablation procedure.
  6. One-year drug-free success defined as freedom from any AF/AFL/AT lasting at least 30 seconds or any Class I or III AAD after removal from antiarrhythmic drug therapy as assessed from the end of the 3-month blanking period to 12 months following the ablation procedure.
  7. Changes in EQ-5D-5L scores from baseline to follow up at 3, 6, and 12 months
  8. Changes in AFEQT scores from baseline to follow up at 3, 6, and 12 months
  9. Cardiovascular-related health care utilization through 12 months post index ablation
  10. Force time integral (FTI) and lesion index (LSI)

NOTE: For endpoints 5 and 6, a full 10-second 12-lead ECG recording of arrhythmia may be substituted for a 30-second recording unless there is evidence that the recorded arrhythmia is short-lived and less than 30 seconds.

